## 10.0 Study Design / Methods

This is a randomized longitudinal controlled observational study using a mixture of qualitative and quantitative methods. The study will recruit 30 participants and utilize a control group experimental design with dependent pretest and posttest to derive data regarding (1) feasibility and (2) within-participant effect size of the RESP-FIT intervention in terms of satisfaction, use and adherence, technical issues and acceptability, and self-reported symptom severity (dyspnea and fatigue). In addition, information satisfying Exploratory Aim 4 (frequency of physical activity) will be obtained. Patient data (Table 1 below) will be collected at baseline, 6 weeks (post-treatment) and 14 weeks (2 month follow up). This study will enable further development of SAMS using our patient centered iterative design guided by feedback from a convenience sample. When completed, 30 adults (15 in each group) will have used SAMS for 6 weeks. (see Fig. 2 Study Design).

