**Randomization and Training Regimen:** Following collection of pre-training baseline measures, participants will be randomly assigned 50/50 to either a Standard of Care (SOC) Control Group (n=15), or a SOC + EMST/IMST Group (n=15). Participant randomization will be stratified by gender and dyspnea grade as measured on the MMRC. Those participants assigned to the SOC control group will receive a Fitbit monitoring device, but no intervention beyond that which is typically provided to patients seen within the MUSC Clinic. Participants randomly assigned to receive SOC+EMST/IMST will receive six weeks of clinician-guided, scripted RMST. This training will be facilitated by the PI using a custom-designed and constructed EMST/IMST trainer. Non-invasive measurement of maximum expiratory and inspiratory pressures (PEmax and PImax; described previously) will be obtained in order to set pressure threshold of the EMST/RMST device. The first week of EMST/IMST training will be conducted with the device set at 75% of the average initial PEmax collected at pre-training baseline. After a nose clip is placed the participants will be taught a four-step procedure: 1) take a breath in, 2) wrap lips tightly around the EMST/IMST trainer mouthpiece, and 3) exhale quickly and forcefully until you hear the popping or whistling sound of the device valve opening, and 4) continue blowing forcefully for two seconds. Once the participant is able to do a five-breath trial, another five-breath trial will be completed with the participant allowed as much independence as appropriate. The participant will receive a text message each day reminding them to complete his or her training and "remain active today." Participants in the SOC group will receive a text message reminding them to "remain active today." The daily training session will be as follows: 1) five sets of five-breath exhalations (25 breaths total) completed each training day, 2) each exhalation within a set will be separated by approximately one minute, and 3) each five-breath training set will be separated by five minutes. A Bluetooth-enabled "use" button on the EMST/IMST device will log the times the participant has used their training device. Each participant will be provided with a diary to record five sets of five-breath training trials on five days each week. Our experience indicates that EMST/IMST takes approximately 20 minutes each day. PEmax will be reassessed weekly, by the research clinician across the six-week treatment period and readjusted to 75% of the participant's current PEmax. If no changes in PEmax are observed week to week, treatment

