
will be continued without increase in the pressure threshold training level. All participants will be managed according to standard treatment protocols used within the MUSC Pulmonary Clinic. Detailed records will be kept pertaining to mortality and morbidity as well as use of inpatient and outpatient hospital facilities, medication use, frequency and duration of disease exacerbations, as well as general response to treatment. All dependent variables will be obtained, for all participants at baseline, mid-intervention (3 weeks post baseline), at intervention end (6 weeks) and 14 weeks (2 months) post baseline.

**Monitoring period:** As per our standard monitoring period with SAMS, participants will receive a daily EMA reminder text. Answering the EMA questions on a smartphone requires 30-45 seconds of time. Probes will occur to not interfere with typical sleep schedule or during school hours. EMA sessions will capture COPD symptoms and emotion/mood over the course of the day. If patients have not filled out an EMA in 3 days, a reminder text will be sent. EMA probe question responses will transfer to RedCap, as TACHL has done with other studies. Data will not be stored on the phone. The participants will be requested to perform video capture of training technique 1 time per week. A reminder will be sent during convenient waking hours if this has not been performed.

**Activity Tracking:** A Fitbit activity tracker will be provided to each participant and comprehensive instruction offered on its use. This activity tracking device is worn on the wrist and only removed for bathing or other activities involving water, as the devices are water-resistant but not waterproof.

**Quantitative and Qualitative Assessments:** Participants will complete quantitative and qualitative assessments of acceptability, feasibility, and performance of the SAM system including:

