**Sample Size:** The purpose of this pilot study is not to confirm or refute hypotheses about treatment effectiveness (with corresponding emphasis on establishment of sufficient power for hypothesis testing); rather, we seek to demonstrate feasibility of the intervention and to obtain estimates of variability for the secondary outcome measures. Therefore, sample size was determined for pragmatic reasons rather than power (Leon, Davis & Kraemer, 2011). For this pilot study, we will recruit approximately 30 patients with COPD and, basing our estimated attrition on previous investigations, we anticipate that approximately 25 of these patients will complete all study-related visits. For this project's secondary aims (continuous outcome measures of self-efficacy, fatigue, and dyspnea), we use an in intent-to-treat analyses and 95% confidence interval (CI) estimates of the within group change scores (pre- to post-treatment) with precisions ranging from  $\pm 0.20$  to  $\pm 0.78$ . These correspond to estimated standard deviations of change scores of these variables, ranging from 0.5 to 2.0.

**Data Management.** Data report forms (DRF) for all data collection will be developed by the PI and study team. The Research Electronic Data Capture (REDCap) system provided through MUSC CTSA will be used to enter questionnaire and measurement data. REDCap is a secure, web-based application designed exclusively to support data capture for research studies. Only authorized study personnel will have access to the data tracking system. Data management including data quality assessment

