#### **14.0 Withdrawal of Subjects**

Participants may voluntarily elect to withdraw their consent at any time for any or no given reason while enrolled in the study. The PI may withdraw participants from the study at any time if they decide it is in the participant's best interest, if they do not follow the investigator's instructions, and/or if they fail to maintain contact with the researchers or attend study visits. Withdrawals of participants may also occur if there is a protocol violation or early study closure. All data gathered from withdrawn participants will be used in the analysis plan under an Intention-to-Treat (ITT) model.

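### The stated 95% CI half-widths for within-group change (±0.20 to ±0.78) fit 25 patients from both arms together; with 12 to 15 patients per arm the same formula gives intervals about 1.3 to 1.4 times as wide.

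*Combined protocol and SAP*

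**What the plan says.** The Sample Size paragraph of section 12.0 (Data Management) explains that "sample size was determined for pragmatic reasons rather than power". About 30 patients will be recruited, and "we anticipate that approximately 25 of these patients will complete all study-related visits". For the secondary outcomes of self-efficacy, fatigue and dyspnea it plans an intent-to-treat analysis and "95% confidence interval (CI) estimates of the within group change scores (pre- to post-treatment) with precisions ranging from" ±0.20 to ±0.78. It ties this range to "estimated standard deviations of change scores of these variables, ranging from 0.5 to 2.0". It does not state the number of patients or the quantile behind the half-widths.

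The design has two arms. Section 10.0 (Study Design / Methods) says that "30 adults (15 in each group) will have used SAMS for 6 weeks". Its paragraph on randomization and the training regimen allocates patients equally to a "Standard of Care (SOC) Control Group (n=15), or a SOC + EMST/IMST Group (n=15"). Only the second arm receives the respiratory training; controls receive an activity tracker and usual care.

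**The concern.** A within-group interval in a two-arm trial is most naturally an interval for one arm, and an arm here has at most 15 patients. The stated half-widths look too narrow for that, and the only number near them in the same paragraph is the 25 completers expected from the whole trial.

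This matters because the paragraph disclaims power, so these half-widths are its only quantitative statement of what 30 patients can deliver on the secondary outcomes. Sections 1.0 and F say that the pilot is meant to inform a larger efficacy trial. A reader planning that trial would expect tighter per-arm estimates of mean change than this design can give.

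**Working it through.** **Inputs.** Confidence level 95%, SD of change 0.5 to 2.0, stated half-widths ±0.20 to ±0.78, about 30 recruited and about 25 completers (section 12.0, Sample Size). Allocation 15 and 15 (section 10.0).

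**Formula.** Half-width = q × SD / √n, where q is the normal quantile 1.96 or the t quantile on n − 1 degrees of freedom.

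**Reproducing the plan's figures.** With q = 1.96 and n = 25:

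- SD 0.5: 1.96 × 0.5 / 5 = 0.196, which rounds to 0.20.
- SD 2.0: 1.96 × 2.0 / 5 = 0.784, which rounds to 0.78.

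**Is 25 the only n that fits?** Solving for n as (1.96 × SD / half-width)² and allowing for rounding:

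- ±0.20 at SD 0.5 (0.195 to 0.205) implies n from 22.9 to 25.3.
- ±0.78 at SD 2.0 (0.775 to 0.785) implies n from 24.9 to 25.6.

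The only whole number in both ranges is 25. The t quantile never matches both ends: n = 27 gives 0.20 and 0.79, and n = 28 gives 0.19 and 0.78. All 30 patients with the normal quantile give 0.179 and 0.716. So the calculation used n = 25 and a normal quantile. This is inferred from the match, since the document does not say so.

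**Per arm.** The 12 and 13 are 25 completers split as evenly as possible. The ratio compares each half-width with the unrounded stated value (0.196 or 0.784).

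| n in the arm | Normal, SD 0.5 | Normal, SD 2.0 | Ratio | t, SD 0.5 | t, SD 2.0 | Ratio |
|---|---|---|---|---|---|---|
| 15 | 0.253 | 1.012 | 1.29 | 0.277 | 1.108 | 1.41 |
| 13 | 0.272 | 1.087 | 1.39 | 0.302 | 1.209 | 1.54 |
| 12 | 0.283 | 1.132 | 1.44 | 0.318 | 1.271 | 1.62 |

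Example for n = 15: 1.96 × 2.0 / √15 = 1.012, and √(25/15) = 1.29.

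The normal columns isolate the effect of using the wrong n. Moving to the t quantile is a separate and smaller effect: it adds 9% at n = 15 (1.108 / 1.012 = 1.09) and 12% at n = 12 (1.271 / 1.132 = 1.12).

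**Which n applies to change at week 6?** The 25 must complete every visit, and measurements are due "at intervention end (6 weeks) and 14 weeks (2 months) post baseline". A patient lost after week 6 still contributes to pre- to post-treatment change. Section 14.0 adds that "All data gathered from withdrawn participants will be used in the analysis plan under an Intention-to-Treat (ITT) model". With even attrition, the n per arm therefore lies between about 12 and 15. No value in that range gives the stated figures.

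**The case against.** The strongest counter-argument is that the phrase within group may mean change within patients over the whole sample. Section 10.0 speaks of a within-participant effect size, section 12.0 describes comparisons before and after treatment without naming arms, and nothing explicitly plans per-arm estimates. On that reading ±0.20 to ±0.78 is arithmetically right and only the wording is at fault. The reading is possible but weak. Section 10.0 ties the effect size to the RESP-FIT intervention, and a change averaged over trained and untrained patients does not estimate it. Nothing plans to pool the arms. Even if pooling was meant, the sentence should say so, and it remains true that neither arm has this precision.

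Three smaller objections have some force.

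- The range of 12 to 15 rests on even attrition. If all five losses fell in one arm, that arm would have 10 patients, and the normal formula would give ±0.31 to ±1.24 (√(25/10) = 1.58 times the stated width). Keeping withdrawn patients' data also does not create a missing post-treatment value, and the plan names no imputation method. Both points could make the intervals wider than shown, so they do not rescue the stated figure.
- Using a normal quantile for a planning figure is partly a matter of preference. That is why the two effects are shown separately; the finding stands on n alone.
- The practical consequence is small. The primary analyses concern satisfaction, fidelity and adherence, and a planner will mainly use the SDs and intervals the pilot actually observes. This limits the importance of the point without making the stated figure correct.

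**Conclusion.** The concern holds. The stated precision is that of 25 patients pooled over two arms, and it is too narrow for either arm. By the plan's own formula the per-arm half-widths are 1.29 times as wide with 15 patients and 1.39 to 1.44 times with 13 to 12. With a t quantile they are 41% (n = 15) to 62% (n = 12) wider than the unrounded stated values.

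This rests on reading within group as per arm, on the plan's own SDs, and on even attrition for 12 to 13 per arm. The match to n = 25 is firm; the per-arm reading is the natural one but is not spelled out in the document. The error affects a stated figure only. It does not undermine the choice of 30 patients, the planned analyses, or the aim of estimating the variability of change.

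**What to change.** Replace the precision sentence in the Sample Size paragraph with one that names the arm, the n and the quantile, for example:

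> 95% CI half-widths for mean pre- to post-treatment change within each arm (t quantile, SD of change 0.5 to 2.0) are ±0.28 to ±1.11 with 15 patients per arm analysed, and ±0.32 to ±1.27 if 12 per arm have data (even attrition assumed).

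If the sponsor prefers to keep the normal quantile, the corresponding figures are ±0.25 to ±1.01 and ±0.28 to ±1.13, and the quantile should be stated. Keep N = 30.

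The cost is one sentence and a less favourable stated precision. No extra patients are needed, and nothing changes in the analysis or conduct of the trial.

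### The secondary analysis is labelled intention-to-treat but specified as pre-post change scores, with no method for participants who lack a week-6 value

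*Combined protocol and SAP*

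**What the plan says.** The Sample Size text in Section 12.0 covers the continuous secondary outcomes in one sentence, which names an intention-to-treat analysis and "95% confidence interval (CI) estimates of the within group change scores (pre- to post-treatment"). It adds, of the precision quoted there (±0.20 to ±0.78), "These correspond to estimated standard deviations of change scores of these variables, ranging from 0.5 to 2.0".

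On numbers, the same paragraph says "we will recruit approximately 30 patients with COPD" and "we anticipate that approximately 25 of these patients will complete all study-related visits".

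Section 14.0 is explicit about people who leave: "All data gathered from withdrawn participants will be used in the analysis plan under an Intention-to-Treat (ITT) model".

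On timing, the opening of Section 10.0 identifies post-treatment with week 6 and lists collection at baseline, week 6 and week 14. The Randomization and Training Regimen text in that section adds a mid-intervention assessment at week 3 for all dependent variables.

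The Statistical Analysis text, the Sample Size text and Section 14.0 name no imputation rule, no repeated-measures model and no definition of the analysis set.

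**The concern.** The label and the statistic do not fit together. A pre-post difference cannot be formed for someone with no post-treatment value, whatever else that person provided. Without a rule for filling or modelling the gap, an analyst who follows the text will compute the difference in those who have both values. A participant measured at baseline and week 3 who then leaves adds nothing to the estimate of change, although those values were gathered.

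The stakes are modest but real. The pilot's stated purposes include estimates of variability for the secondary outcomes, and Sections 1.0 and 13.0 (Interim Analysis) say that the results will shape a larger efficacy trial. If leavers respond differently from those who stay, both the mean change and its SD describe a selected group, under a label that tells readers otherwise.

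Some features of the plan make it plausible that leaving is related to outcome. Sections 4.0 and 14.0 allow the investigator to withdraw participants who do not follow the protocol or instructions. The adverse-event example in Section 13.0 involves withdrawal after symptoms that may reflect an exacerbation. Only one arm carries the training burden.

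**Working it through.** **Inputs.** From the Sample Size text in Section 12.0: about 30 recruited, about 25 expected to complete all visits, SD of change 0.5 to 2.0, stated half-width ±0.20 to ±0.78. From Section 10.0: 15 per arm. Assumed, because the documents give nothing: a difference d of 0.5 to 1 SD between the mean change of leavers and of completers.

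**1. Reproduce the stated precision.** Half-width = 1.96 × SD / √n.

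- n = 25: 1.96 × 0.5 / 5 = 0.196, and 1.96 × 2.0 / 5 = 0.784. These round to the stated 0.20 and 0.78.
- n = 30: 0.179 and 0.716 (with t quantiles, 0.187 and 0.747). No match.
- n = 15: 0.253 and 1.012 (with t quantiles, 0.277 and 1.108). No match.

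Over n = 10 to 34, with normal and t quantiles, only the normal quantile with n = 25 gives both figures. Working backwards from 0.78 with SD 2.0 and allowing for rounding, n lies between 24.9 and 25.6. The precision attached to the intention-to-treat analysis is therefore computed on the expected completers.

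**2. How many could be left out.** 30 − 25 = 5, and 5/30 = 16.7%. The 25 are those expected to finish every visit, including week 14. Someone lost between weeks 6 and 14 still has a week-6 change score. Five is therefore roughly an upper figure for missing week-6 values.

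**3. Possible shift in the mean change.** Shift = fraction missing × d.

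- Arms pooled: 5/30 × 0.5 = 0.083 SD; 5/30 × 1 = 0.167 SD.
- Extreme case, all five in one arm of 15: 5/15 × 0.5 = 0.167 SD; 5/15 × 1 = 0.333 SD.

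These scale down in proportion if fewer than five lack week 6.

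**4. Possible effect on the variance.** If leavers and completers have the same spread around their own means, the variance in everyone is 1 + p(1 − p)d² times that in completers. With p = 1/6, p(1 − p) = 5/36 = 0.139, so the excess is 0.139 × 0.25 = 0.035 for d = 0.5, and 0.139 for d = 1. A later sample size built on the completers' variance would be too small by a factor of about 1.03 to 1.14 under this assumption.

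**The case against.** The strongest reply is that this is an unspecified detail and not a contradiction. A within-group change with a confidence interval can be estimated under intention-to-treat by imputation or from a repeated-measures model, and planning precision on expected completers is ordinary caution. Part of this stands. A reader might infer that the plan prescribes a complete-case analysis. It never uses that term or an equivalent, and the match with n = 25 does not by itself fix the analysis set. What remains is that the only statistic specified needs a week-6 value, and nothing says how anyone without one is to be included.

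A reader might also infer that five people will certainly be dropped. The documents do not support that, because the attrition figure covers all visits through week 14.

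A third tempting inference is that the completer mean overstates benefit. The documents give no reasons for the expected attrition and no comparison of leavers with completers. Overstatement is plausible but not established. The all-in-one-arm figure is an extreme case. With 12 to 13 per arm, the 95% half-width is about 0.60 to 0.64 SD (t quantiles). With 10 left in an arm it is about 0.72 SD. The possible shifts lie inside these intervals.

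It is also fair to say that these are secondary outcomes in a feasibility pilot, that leavers' baseline values still enter the descriptive statistics, and that week-3 values are uncertain. The measures tables in Section 10.0 list respiratory pressures only at baseline and the second visit, and the St. George's questionnaire only at baseline and after the intervention. These points limit the size of the problem and do not remove it.

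**Conclusion.** The point holds. As written, the change-score analysis can use only participants with a week-6 value. That does not deliver the intention-to-treat label in Section 12.0 or the commitment in Section 14.0 to use withdrawn participants' data. Two things rest on the documents alone: the absence of any missing-data method, and the reproduction of the stated precision at n = 25 only.

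The size is less certain. Up to about 5 of 30 are affected. The consequence, in either direction, is up to about 0.08 to 0.17 SD in the pooled mean change, and up to 0.33 SD in the extreme one-arm case. Both figures depend on the assumed gap of 0.5 to 1 SD. The primary feasibility analyses are not touched.

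**What to change.** Estimate the secondary outcomes with a linear mixed model on all randomised participants, using every available value: baseline, week 3 where collected, week 6 and week 14. Include arm, time, arm by time, and the randomisation strata (gender and MMRC dyspnea grade). Report the within-arm change at week 6, which keeps the plan's own quantity. Also report the between-arm difference in change, which uses the control group that Section 3.0 adds because a tracker alone may affect activity. Give 95% confidence intervals for both. Keep the completer change score as a sensitivity analysis, and state which outcomes are measured at week 3.

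The cost is some rewording of the analysis section and slightly more analysis; no new data are needed. The model removes bias only if missingness depends on observed data, and a participant with a baseline value alone adds little information about change.

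If the change-score analysis is kept as the main one, call it completer-based and drop the intention-to-treat label.

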### **13.0 Provisions to Monitor the Data to Ensure the Safety of Subjects**

There is a well-developed and NIH/NINR prepared DSMP that involves the use of a Safety Monitoring Committee (SMC) that shall meet semi-annually post initial study enrollment. The Committee is comprised of key individuals that include: an independent safety monitor (ISM), a biostatistician (BS), and the Program Manager (PM). Post initial study enrollment, the SMC will convene semi-annually and all reports will be forwarded to the IRB and Sponsor in accordance with institutional policies and sponsor requirements.

